5.2 Locator/Contact Information

Once the participant is consented, designated site study staff will complete a Contact Information Worksheet with the participant and/or enter the participant's contact information directly into SMART Web during the enrollment visit. Participants will also be asked to provide social media contact information, if the participant is willing. Participants will be asked to provide a working phone number or valid email address through which they can be reached. Participants will also be asked to provide valid contact information for a family member and/or friend who can be called in the event the participant cannot be reached by phone or email. Participants will be asked if messages can be left at the numbers provided. Study staff will not leave messages unless expressly permitted to do so by the participant which also will be documented on this form. If permission is given to leave messages, site study staff will assure participants that messages left with a family member or friend will only ask the participant to contact study staff and will not include any protected health information or information related to study participation.

The Contact Information Worksheet will not contain any study data and will be entered into the SMART system and maintained under double locks at the study site, separate from all study records, with access limited to designated site research personnel.

5.3 Randomization Procedures

Randomization will be used only for the pilot RCT. Only participants who express interest in using LYNX, meet eligibility criteria, provide informed consent, and complete a baseline assessment will be eligible for randomization. Subjects will be randomized 2:1 into either the LYNX intervention arm (N=40) or control arm (N=20).

The 2:1 allocation will allow us to efficiently gather additional data on app utilization. Randomization will be based on a pre-generated list created by the Analytic Core, with random blocks of size three or six, and stratified by site (Tampa, Chicago) and age (15-18, 19-24). After consent and baseline survey completion, the participant will be randomized (assigned to the next available random allocation). **LYNX Intervention Condition:** Individuals who receive LYNX will be given brief instructions on the purpose of the app, how to access it, and an overview of how to use it. Participants will be encouraged to explore all components of the app and use it routinely. **Standard of Care Condition:** Following screening, participants in both conditions will receive standard of care prevention material consisting of provision of information regarding recommendations for HIV testing and referrals to local HIV testing sites and prevention services.

5.4 Intervention/Investigation Procedures

5.4.1 Formative phase (Aim 1)

To refine the LYNX app, we will use an iterative development design with focus groups (FG) and/or in-depth interviews (IDIs) with 8-10 YMSM at each of two study sites, followed over 3-6 months (up to 3 iterations). Using a discussion guide, we will demonstrate the app and wireframes (screenshots) of new components and elicit perspectives in content, layout, usability, and functionality. The IMB domains described above will guide the development process. New content to promote PrEP uptake may include PrEP educational and testimonial videos, curated information and links to PrEP websites and discussion forums (PrEP information); information about how one's Sex Pro score could improve on PrEP (PrEP motivation); a map with PrEP-friendly youth providers, and an online navigator to assist with troubleshooting PrEP access issues (PrEP behavioral skills). We will also elicit feedback on the HIV/STI testing kit and instructions. We will also investigate preferences for documentation of clinic or home-based HIV/STI testing (release of medical records, taking pictures of test results through app). Participants will be asked to download and test iterative versions of the app for two weeks prior to the next FG or IDI where we will gather feedback on the usability, design, and potential impact of the app. Study staff will use an onboarding document to walk participants through the download procedures and use of the app. FGs and IDIs may be conducted in person, or via video-conferencing. Participants will be reimbursed for completion of each FG or IDI according to local site guidelines.

All FGs and IDIs will be conducted by the LYNX team/study site members and video-recorded for transcription and analysis using Transana software by UCSF/SFDPH study staff. The goal of the analysis is to identify barriers and facilitators to app usability. If available, members of the app development team from Apt Mobility will observe the focus groups via video-conference in case they need more clarification of specific suggestions for improving the app. Analysis of the FG will commence immediately after participants leave in the form of a discussion of salient themes and suggestions among UCSF/SFDPH study staff and the Apt Mobility team. The team will then prioritize changes to the app for the next iteration to be tested and discussed in the next round of focus group discussions. Recordings will be stored on a secure hard drive in a locked cabinet. Analysis of the focus groups in Transana does not require a transcript since the codes are applied to the timeline of the video rather than line numbers in the transcript. If further transcription is necessary, selected segments of the video and audio interview data from the FGs and IDIs will be transcribed by Paul M Garton, Inc., a transcription company with whom we have worked with for the past ten years.

The LYNX app will be refined by **Apt Mobility** (www.aptmobility.com), the development team who created the original version of the Sex Pro app and has extensive experience creating health-related apps with the UCSF mHealth group. The LYNX app will be developed for both iOS and Android platforms simultaneously, the two mobile phone platforms that make up more than 90% of smart phones in the U.S.

5.4.2 Technical pilot (Aim 2)

After revisions to the LYNX app are completed based on the formative phase, we will conduct a 2 month, single-arm, pilot study among 12-15 YMSM across two iTech sites to optimize the technical performance and functionality of LYNX. YMSM who participated in the formative phase may participate in the technical pilot. At an in-person enrollment visit, YMSM will download the LYNX app and answer an online computer assisted self-interview (CASI) questionnaire on sociodemographics, use of

technology, and risk behaviors. Study staff will walk participants through the download procedures and use of the app. Participants will then be encouraged to use all app components over the next two months, including ordering and using the HIV/STI testing CareKit at least once during the technical pilot. The study will follow the STI and HIV CareKit, Condom, and Lubricant Ordering Standard Operating Procedures developed by the CareKit team at Emory. Additionally, the study will also request participants to sign medical release forms for the release of their official testing results from the respective testing site so that study staff can collect official results. Upon completion of the technical pilot, all participants will complete an online exit interview with qualitative-trained study staff to provide feedback on functionality, technical performance, errors and bugs encountered, overall experiences using the app, feasibility and acceptability of methods to confirm HIV testing results, and feedback for further refinement. Online interviews will be conducted using a HIPAA-compliant, video-chat application that provides strong security components and is easy to use across multiple devices. We will also assess preliminary usability and acceptability of the app using the System Usability Scale, a validated assessment tool assessing various domains of the app with demonstrated high internal consistency across a number of studies. Participants will also complete a computer assisted self-interview (CASI) to assess these measures, along with changes in risk behaviors during the study. Participants will be given the option to return to the SRV to complete the online exit interview and CASI or complete them online. Participants will be reimbursed for the enrollment visit and exit interview/CASI according to local study site guidelines. All exit interviews will be recorded and transcribed for analysis.

Participants who seroconvert during Aim 2 (two month technical pilot) will be offered a referral for HIV care, including confirmatory HIV testing and linked to HIV care if confirmatory testing is positive; continue to have access to the app, and be invited to complete the follow-up CASI assessment and the exit interview. A referral for linkage to care will be offered by the SRV clinic. A set of questions will be asked regarding the participant's experience, particularly as it pertains to app use and linkage to care.

5.4.3 Pilot RCT (Aim 3)

5.4.3.1 Screening and Enrollment

Potentially eligible participants will attend an enrollment visit where eligibility is confirmed, the details of the study will be explained, and informed consent obtained. Participants who participated in formative and/or technical pilot phases of this study will not be allowed to participate in the pilot RCT. Eligible participants will complete a baseline computer assisted self-interview (CASI) of HIV risk behavior, HIV/STI knowledge, utilization of STI/HIV prevention services, PrEP knowledge and attitudes, psychosocial measures (including depression, substance use, stigma, social support), and HIV risk perception and will be enrolled in the study on the same day if possible. Participants will be randomized to receive LYNX (intervention) vs. the standard of care (control) in a 2:1 ratio (see randomization procedures in section 5.2). This design was chosen to maximize collection of acceptability data among app users. Participants who have completed the baseline assessment, have been randomized, and complete app onboarding (intervention arm) or receive the standard of care information about HIV/STI testing and PrEP (control arm) will be considered enrolled in the study. All enrolled participants will receive counseling on the importance of HIV testing per local testing guidelines.

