3.0 STUDY DESIGN

Using an iterative process of app development, this study will be conducted in 3 phases: 1) formative research to refine LYNX with input from YMSM; 2) a technical open pilot to optimize functionality and technical performance; and 3) a pilot RCT to evaluate feasibility, acceptability, and preliminary efficacy of LYNX.

- **Formative Phase**

Guided by the IMB model, the LYNX app will be refined through an iterative design process informed by a series of focus groups and in-depth interviews in up to 40 YMSM to elicit feedback on content, usability, layout, and functionality of the LYNX app.

- **Technical Pilot**

The LYNX app will be tested in a 2 month technical pilot study in up to 15 YMSM to optimize app functionality and performance. Data will be used to further refine the app and finalize the intervention protocol, outcome measures, and assessment tools for the pilot RCT.

- **Pilot RCT**

60 HIV-uninfected YMSM will be enrolled into a 6 month pilot study evaluating the feasibility and acceptability of the LYNX app. Participants will be randomized 2:1 to receive the LYNX app or a standard of care control condition. Feasibility and acceptability will be assessed through app analytics of usage patterns (logins, use of app components) and acceptability scales administered via computer-assisted self interview. We will also evaluate preliminary efficacy by comparing the proportion of YMSM who test at least once during the 6 month pilot, and proportion who successfully link to a PrEP provider, in the intervention versus control groups.

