5.0 STUDY PROCEDURES

5.1 Enrollment procedures

Individuals who screen eligible will be contacted and scheduled for an in-person visit to the SRV at the participant's earliest convenience. SRVs will also have the option to have the participant complete the online screener the day of the visit. During the visit, the eligibility of the participant will be confirmed, details of the study will be explained and informed consent/assent obtained.

Individuals who do not consent or assent to participate will be asked if they are willing to provide their reason for declining participation; responses will be recorded on a CRF. Individuals assessed as ineligible for enrollment will have the reason(s) for ineligibility recorded.

The study team may request tabulated information on individuals who participated in the enrollment process, but did not provide informed consent/assent and the reasons these individuals refused to participate. These data will provide general information on the population that is recruited at the SRVs into the study

After informed consent/assent is obtained, the participant will complete a CASI baseline assessment. For Aim 3, randomization will only occur AFTER a baseline assessment is completed.

In Aim 3, participants assigned to the intervention group will be considered enrolled in the study after they have completed the baseline assessment, been randomized, and completed app onboarding (for

the intervention arm). Participants assigned to the control arm will be considered enrolled in the study after they have completed the baseline assessment, been randomized, and been given standard of care materials.

CRFs will be completed by study staff to capture the participant's eligibility and enrollment.

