5.6 Intervention Monitoring/Quality Control

A study checklist will be used to ensure that the research staff member assists participants in downloading the app, provides instruction on its use, and explains the relevant app features and sets up customizable features (e.g., reminders for HIV testing).

App analytics, including logins to the app and use of different app components, will be monitored for the technical pilot and pilot RCT phases of this project. Any issues that are detected will be discussed with the protocol team and site research staff, and a remediation plan will be developed and implemented at the sites.

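### Testing counselling meant for both arms is tied to a status reached only after open allocation; move it before allocation is released

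*Combined protocol and SAP*

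**What the plan says.** For the pilot RCT, Section 5.4.3.1 states: "All enrolled participants will receive counseling on the importance of HIV testing per local testing guidelines". The sentence just before it defines enrolment: "Participants who have completed the baseline assessment, have been randomized, and complete app onboarding (intervention arm) or receive the standard of care information" count as enrolled. Section 5.1 gives the same definition. For the control arm a man must have "completed the baseline assessment, been randomized, and been given standard of care materials"; for LYNX the last step is app onboarding.

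Section 5.3 adds a separate item: "Following screening, participants in both conditions will receive standard of care prevention material consisting of provision of information regarding recommendations for HIV testing", together with referrals to local services. Section 5.4.3.3 gives controls further content of their own: an instruction to use existing testing sites, a list of those sites and a PrEP brochure.

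Section 5.4.3.2 has study staff carry out the LYNX onboarding. No section describes blinding of staff, and none says who gives the counselling, for how long or from what script. The quality-control step in Section 5.6 reads: "A study checklist will be used to ensure that the research staff member assists participants in downloading the app". It goes on to instruction, features and reminders, and does not mention the counselling.

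Section 6.3.3 measures testing as the proportion who self-report at least one test in follow-up. Comparing testing between arms is a secondary objective (Section 2.2). The starred primary endpoints are the System Usability Scale and opening of the app.

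**The concern.** The counselling urges men to do what the testing outcome counts. Its stated subject is the same for both arms, so it does not need to wait for the allocation. Under the protocol's own definition of enrolment it does wait, and by then the arm is open to the staff who handle the visit.

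Two things follow. First, delivery could differ by arm. A staff member who has just walked a man through reminders and test kits might say more, or less, than to a control. Section 5.3 randomises only men who express interest in using LYNX, so staff might also try to make up for its absence. The direction cannot be predicted, and no script or checklist entry would prevent or record it.

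Second, receipt of the counselling depends on an arm-specific step after randomisation. A control need only be handed information. A man in LYNX must complete onboarding, and if he does not, the counselling sentence does not cover him. This asymmetry lies in the wording and needs no assumption about how staff behave.

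**Working it through.** **1. Order of events, read from the text**

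| Step | LYNX | Control | Source |
|---|---|---|---|
| Baseline CASI | before randomisation | before randomisation | 5.1 |
| Randomisation | then | then | 5.1, 5.3 |
| Step that completes enrolment | app onboarding | standard-of-care information or materials | 5.1, 5.4.3.1 |
| Testing counselling | all enrolled | all enrolled | 5.4.3.1 |

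No section places the counselling before randomisation. It follows onboarding in LYNX only, because controls have no onboarding.

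**2. The plan's own figure**

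Section 10.1.3 gives 80% power to detect 37-42 points with 60 men, 2:1 allocation and 10-20% attrition. It states neither the significance level nor the control rate. I assume two-sided 5%, z = 1.96, and the usual normal approximation:

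- power = Φ[(d − z·SE0)/SE1], with d = p2 − p1
- SE0 = √[p̄(1−p̄)(1/n1 + 1/n2)], with p̄ = (n1·p1 + n2·p2)/(n1 + n2)
- SE1 = √[p1(1−p1)/n1 + p2(1−p2)/n2]
- n1 = 20 × 0.9 = 18 or 20 × 0.8 = 16 controls; n2 = 36 or 32

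Control rates of 15-45% give detectable differences of 37.3-39.3 points at 10% attrition and 39.1-41.5 at 20%. This agrees with the plan's 37-42, subject to the assumed level and rates.

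**3. Equal counselling in both arms**

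If both arms gain equally and the app does nothing, the rates stay equal and the rejection rate stays at 5%. Suppose the counselling lifts the control rate from 20% to 50%. The detectable difference then moves from 38.8 to 35.9 points (10% attrition) or from 41.1 to 37.6 (20%). Shared delivery is harmless to validity.

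**4. Unequal counselling (assumed)**

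Assume no app effect, a control rate p of 20-50%, and b extra points of testing in LYNX alone. With p1 = p and p2 = p + b:

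- rejection rate = Φ[(b − z·SE0)/SE1] + Φ[(−b − z·SE0)/SE1]
- spurious risk ratio = (p + b)/p

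Worked case: p = 0.30, b = 0.10, n1 = 18, n2 = 36.

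- p̄ = (5.4 + 14.4)/54 = 0.367
- SE0 = √(0.367 × 0.633 × 0.0833) = 0.139
- SE1 = √(0.21/18 + 0.24/36) = 0.135
- rejection rate = Φ(−1.28) + Φ(−2.75) ≈ 0.101 + 0.003 = 0.104
- risk ratio = 0.40/0.30 = 1.33

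| b (points, LYNX only) | Rejection rate, p = 20-50%, both attrition levels | Spurious risk ratio, p = 20% to 50% |
|---|---|---|
| 0 | 5% | 1.00 |
| 5 | about 6% | 1.25 to 1.10 |
| 10 | 10-11% | 1.50 to 1.20 |
| 15 | 16-19% | 1.75 to 1.30 |
| 20 | 25-30% | 2.00 to 1.40 |

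**5. The opposite direction (assumed)**

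If true testing were 50% in LYNX and 30% in controls, the ratio is 50/30 = 1.67. Extra counselling worth 5 or 10 points in controls (1 or 2 of 20 men) lowers it to 50/35 = 1.43 or 50/40 = 1.25.

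None of the values of b, or the 50% and 30%, comes from the documents. Steps 4 and 5 show sensitivity; they do not estimate a bias.

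**The case against.** **The timing is inferred.** The counselling sentence names a population, not a moment. Section 3.0 uses the word more loosely: "60 HIV-uninfected YMSM will be enrolled into a 6 month pilot study", with randomisation mentioned afterwards. That is fair, but the operative definition stands directly before the counselling sentence and is repeated in Section 5.1, so the literal reading is the natural one. That the counsellor knows the arm is likewise an inference from open onboarding and the absence of any blinding.

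**A shared co-intervention does not bias a randomised contrast.** Correct, and step 3 confirms it. Bias needs delivery that differs by arm, and the documents show none. Site differences in local guidelines are balanced by stratification on site, and Section 5.5 trains staff in study procedures. What stands is a risk without a safeguard.

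**A reader might infer that the documents contradict themselves on the standard-of-care material**, since Section 5.3 says "Following screening, participants in both conditions will receive standard of care prevention material" while Section 5.1 places it after the man has "been randomized, and been given standard of care materials". They do not: anything given after randomisation is also given after screening. **A reader might also infer that everything said at this visit is the same for both arms.** It is not; the content of Section 5.4.3.3 belongs to controls and can stay after allocation.

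**The noise is larger than the effect.** For 20/40 v 6/20, the log risk ratio has SE √(1/20 − 1/40 + 1/6 − 1/20) = 0.376, so 1.67 has an approximate 95% interval of 0.80-3.49, which contains the values in step 5. This stands, and Section 10.1.3 already concedes low precision. It limits the importance of the point, but a possible distortion that can be removed at no cost need not be added to the noise.

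**Onboarding will seldom fail.** Section 4.2 excludes men unwilling or unable to download the app, so few are likely to fall into the coverage gap. The gap in the wording remains.

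**Reordering closes only one contact.** True. Staff who know the arm still onboard LYNX men and instruct controls.

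**Conclusion.** This is a cheap improvement, not a demonstrated bias. Read literally, counselling common to both arms comes after open allocation, depends on an arm-specific step, and is not on the checklist. Nothing prevents or records delivery that differs by arm.

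A reader might conclude that the testing comparison is biased, or that its direction is known. The documents support neither: unequal delivery is not shown, and it could push the ratio either way. The size cannot be computed. Under the stated assumptions, a 5-point excess in LYNX hardly matters (rejection about 6%), 10 points roughly doubles the nominal 5%, and 20 points gives 25-30%. These figures rest on an assumed two-sided 5% level, control rates of 20-50% and no app effect.

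The consequence is confined to the secondary, self-reported testing comparison. The primary endpoints are judged on point estimates in app users and are not the concern. The point still deserves action because Section 10.1.3 says that the efficacy results will be read for pattern and plausibility, where a distorted point estimate could mislead.

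**What to change.** In Sections 5.1, 5.3 and 5.4.3.1, set one order for the Aim 3 visit:

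1. consent or assent;
2. baseline CASI;
3. testing counselling (content still per local guidelines) and the prevention material that Section 5.3 gives to both conditions;
4. release of the allocation;
5. arm-specific steps: onboarding for LYNX; the instruction, site list and PrEP brochure of Section 5.4.3.3 for controls.

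In Section 5.4.3.1, replace *All enrolled participants* with *All consented participants, after the baseline CASI and before randomisation* (assent included for minors). Add one line to the Section 5.6 checklist confirming that counselling was given before allocation was released.

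Placing the talk after the CASI leaves baseline answers untouched. Placing it before allocation means that every randomised man receives it from someone who does not yet know his arm. Sample size and the 37-42 point detectable difference do not change.

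The cost is a reordering within the same visit, one checklist line, and a few minutes of counselling for any man who is then not randomised. Arm-aware contact during the arm-specific steps remains, as it must in an open app trial.
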